7.1 Component 1: Exercise

The instructional part will be delivered via average twice weekly, one-hour, in-person home, center-based, or virtual (via HSL's Zoom video-conferencing software) physical therapy sessions, depending on the patient's preference, familiarity with technology, availability of transportation, and other contingencies (e.g., COVID-19 based restrictions, incremental weather). Evidence suggests that virtual sessions offer similar benefits to in-person home sessions³⁰ or in-clinic sessions.³¹ Although a twice-weekly schedule is aimed, the schedule will be adjusted flexibly to deliver a total of 6-8 sessions.

Exercises targeting flexibility, strength, and endurance will be adopted mainly, though not exclusively, from the NIA Go4Life guide (<https://go4life.nia.nih.gov/>). Sample exercises are shown in **Table 4**.

Before each in-person or virtual physical therapy session, the study physical therapist will review safe areas for exercise, safety techniques and warning signs (such as chest pain or pressure, severe dyspnea, left shoulder or arm pain, indigestion, heart palpitations, lightheadedness, dizziness, and headache). Participants will begin at a low level of effort and incrementally increase exercise intensity according to the therapist's guidance. For virtual sessions and self-directed exercise, we will ask caregivers, family members, or home health personnel to provide supervision for safety and development of adverse events, whenever possible. During the in-person session, blood pressure, heart rate, and blood oxygen level will be monitored by the physical therapist.

The self-directed part will include self-directed exercise (any types of exercise) at least 30 minutes per day for 4 or more days per week. Step count data from a wearable device (Fitbit Fitness Tracker) will monitor progress and provide feedback, which improves adherence in older adults. Fitbit Fitness tracker will either be provided at the pre-admission testing visit or mailed to the patient's home.

Table 4. Sample exercises for flexibility, strength, and endurance (source: Go4Life)

Flexibility (stretching)	Strength	Endurance

• Neck• Shoulder• Shoulder and upper arm• Upper body• Chest• Back• Ankle• Back of leg• Thigh• Hip• Calf	
• Hand grip• Wrist curl• Arm raise• Arm curl• Seated row• Wall push-up• Elbow extension• Chair dip• Leg raise• Knee curl• Leg straightening• Chair stand• Toe stand	
• Walking

7.2 Component 2: Nutrition

The instructional part will be delivered in once-weekly (on average), one-hour, virtual group sessions (via HSL Zoom software) by co-investigator/registered dietitian, [name], (the virtual sessions will be offered at three different days/times to accommodate participants' schedules). This nutrition counseling will focus on optimal protein intake (1.2 gram per kg of body weight) for lean body mass preservation (from food sources and oral nutritional supplements). Sessions will focus on nutrition for muscle gain and lean body mass preservation with topics including:

- *Session 1:* Good sources of protein and total needs (1.2 grams x weight in kg)
- *Session 2:* Protein intake timing: rule 15/30 (at least 15 grams within 30 minutes of exercise)

- Session 3: Protein for muscle gain
- Session 4: Tips to increase protein intake

The self-directed part will include consumption of oral nutritional supplements (20-30 grams of protein/day and between 150-350 calories/day, such as Think! High Protein Bar (20 grams protein, 22 grams carbohydrate, 150 calories) or Ensure Enlive (20 grams protein, 45 grams carbohydrate, 350 calories) , which will be provided by our study team. Oral nutrition supplements (ONS) will be ordered directly from the product manufacturer in bulk and mailed to the patient's home by a research assistant. Due to ongoing supply chain shortages of popular nutrition supplements, we have identified multiple that meet the above macronutrient parameters. All supplements will be purchased in bulk for each participant with enough to last the entirety of the study. Supplements will not be changed unless the patient reports an adverse event such as GI distress (please see section *B5* for more detailed information). Protein supplements are shelf-stable and can be stored at room temperature until use by date when unopened. Once opened, product should be refrigerated within 4 hours. After opening, any remaining product should be discarded within 48 hours – though patients will be encouraged to consume product in its entirety within 24 hours per study protocol.

Patients with chronic kidney disease stage 3 or higher will not receive this intervention because high protein intake may accelerate kidney function decline. This will be determined by medical record review (medical history of chronic kidney disease or elevated creatinine value within the last 6 months) and/or lab results obtained before the start of the study intervention.

7.3 Component 3: Meditation

The instructional part will be delivered in once-weekly (on average), one-hour, virtual group sessions by a meditation teacher, [name], at BIDMC Sadhguru Center (the virtual sessions will be offered by BIDMC Zoom video-conferencing at three different days/times to accommodate participants' schedules). Classes will focus on breathing techniques, yoga, and mindful meditation practices.

The self-directed part will include practicing self-directed meditation for a minimum of 12 minutes daily.

7.4 Component 4: Cognitive Behavioral Interventions

A trained co-investigator will have (on average) once weekly 0.5-hour telephone-based sessions with individual patients to deliver cognitive behavioral strategies to increase adherence to the prehabilitation program. These strategies will include:

- Education about frailty and surgery
- Increase positive beliefs of the benefits of exercise and nutrition
- Discuss barriers

- Set individualized goals for surgery and recovery
- Develop a detailed exercise and nutrition plan (including logistics)
- Self-monitoring of progress using weekly exercise, diet, and meditation logs
- Enhance self-efficacy through the celebration of small wins

This co-investigator has completed the Professional Education Systems Cognitive Behavioral Therapy Intensive Training Course in preparation for this intervention. This course is designed for health professionals without formal cognitive therapy training.

8. STUDY ENDPOINTS/OUTCOMES

8.1 Primary Outcome

For the *primary outcome* we will measure the following:

Feasibility of the prehabilitation program

- Measurement: proportion of patients to whom we can deliver an adequate dose ($\geq 50\%$ of the planned sessions) of the 3 core interventions: physical therapy ($\geq 4/8$ sessions), nutrition ($\geq 2/3-4$ sessions), and meditation ($\geq 2/3-4$ sessions).
- Range: 0-100% (higher values indicate higher feasibility).

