2. OVERVIEW

The purpose of this feasibility pilot study is to understand how a prehabilitation program for older adults with frailty can best be optimized to prepare at-risk patients for major surgery. As such, our program interventions target major risk factors that are modifiable yet rarely addressed in the pre-surgery period (physical function, nutrition, pain, sleep, anxiety, and cognition). We also aim to determine how these interventions can best be delivered for optimal participation.

Participants will receive 3 to 4 weeks of exercise training with a physical therapist, nutrition education with a registered dietitian, meditation with an experienced meditation teacher, and cognitive behavioral intervention to discuss goals, facilitators and barriers to program adherence with the goal to enhance motivation and promote self-efficacy. Two (2) follow-up assessments will additionally be performed at days 30 and 90. Further details of the intervention are provided below:

- Exercise training with home/virtual/in-center physical therapy will take place on average twice a week for 1 hour per session over 3-4 weeks. The participant will be encouraged to exercise on their own for 30 minutes per day for 4 or more days a week and track exercise in a diary (number of minutes achieved per day). They will also be asked to wear a physical activity tracking device (Fitbit Fitness tracker) to measure daily number of steps, active minutes, and heart rate. This device will also remind the participant to get up and move throughout the day.
- Nutrition class with a licensed nutritionist (registered dietitian) will take place on average once a week for 1 hour per session over 3-4 weeks. The participant will also be asked to drink/consume 1 high calorie, high protein nutritional supplement per day which will be provided to them by the study. They will be asked to write down their approximate daily food intake in a diary (3 days/week) – this will be an informal accounting of their intake with the primary focus being on protein-containing food items. This information will be used to measure their protein intake during their participation in the study.
- Meditation with a yoga/meditation teacher will take place once a week for 1 hour per session over 3-4 weeks. The participant will also be asked to practice meditation on their own for at least 12 minutes each day and track in a diary (number of minutes achieved each day).

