- Weekly check-in calls will take place once a week for about 30 minutes per session over 3-4 weeks. During these calls the participant will talk about their goals, discuss personal motivation, and review their progress. They will be asked about any potential adverse events (such as sore muscles or falls).
- A 30 minute telephone interview will take place at the end of the intervention (in weeks 3 or 4). The participant will be asked to provide feedback discussing what parts of the

intervention worked well and what did not. We will use this information for protocol refinement.

The primary outcome is the feasibility of the prehabilitation protocol, defined as the proportion of patients to whom we can deliver an adequate dose ($\geq 50\%$ of the planned sessions) of the 3 core interventions: physical therapy ($\geq 4/8$ sessions), nutrition ($\geq 2/4$ sessions), and meditation ($\geq 2/4$ sessions). Secondary outcomes include 1) adherence to exercise, protein intake and meditation; 2) changes in 5-chair stand time, dominant handgrip strength, patient-centered outcomes, measured using PROMIS scores in physical function, cognitive function, participation in social roles/activities, depression, anxiety, sleep disturbance, pain and fatigue domains at baseline, following completion of the prehabilitation (before surgery), and on postoperative days 30 and 90; 3) clinical outcomes (3-D Confusion Assessment Method,¹ a composite complication score,² length of stay, and 30-day readmission and death); and 4) Postoperative Quality of Recovery Scale³ to be obtained around postoperative day 3; 5) adverse events.

The proposed research will provide necessary information for a larger randomized controlled trial (RCT).

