5. STUDY POPULATION

We will review schedules to identify patients who meet the following inclusion (5.1) and exclusion criteria (5.2). A trained research assistant will perform preoperative geriatric assessment—which consists of 1) medical history (automated in EHR), 2) self-reported functional status (a questionnaire of 22 daily activities and physical tasks), 3) tests of cognitive function (Mini-Cog or MoCA test) and physical function (gait speed, chair stands, and grip strength), and 4) nutritional status (automated in EHR)—and calculate a frailty index using our EHR calculator. For eligible patients, we will explain the purpose of our study to the patients and their surgeon and ask whether they are willing to participate in 3 to 4 weeks of prehabilitation. Remote or e-consent will be obtained. Screening of potential participants will take place during the surgeon’s office visit. The assessment of eligibility will take place by telephone. Our target enrollment is 30 patients (2 patients per week for 15 weeks). See the detailed inclusion and exclusion criteria provided below:

5.1 Inclusion Criteria:

- Patient is ≥ 70 years
- Patient is ≥ 65 years old AND high risks per surgeon’s clinical judgement
- Patient is scheduled to have a gastrointestinal, gynecological oncologic, urologic, and cardiovascular procedure
- Patient provides an informed e-consent or remote consent

5.2 Exclusion Criteria:

- Surgery is scheduled less than 21 days from the expected start date of the prehabilitation intervention
- Patient is considered an inappropriate candidate per the surgeon’s assessment.
- Non-English speaking
- Patient has a major cognitive impairment, which will be defined as telephone Montreal Cognitive Assessment (MoCA) <18 or Brief Capacity Assessment Questionnaire
- Patients with chronic kidney disease stage 3 or higher will be excluded from receiving protein supplement of the prehabilitation intervention.

[figure not shown]

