7. STUDY INTERVENTION

All participants will be enrolled in a prehabilitation program that will start 3-4 weeks prior to the date of scheduled surgery. The intervention will target three principal components (physical activity, nutrition, and meditation) and deliver cognitive behavioral interventions

(Table 3). Each intervention has 1) instructional or training components, delivered by our study team, and 2) self-directed components.

Table 3. Multicomponent prehabilitation program and measures of feasibility and adherence for each component

Target	Intervention	Measures of Feasibility or Adherence
Exercise: Increase muscle function	
 • Physical therapy (home, in-person, hybrid or virtual) 
 • By physical therapists • Average two 1-hour individual sessions per week (delivered in patient's home, in-person center, hybrid, or virtual) • Goal: 6-8 total PT sessions • Endurance, strengthening, flexibility • Self-directed exercise 
 • Goal: 30 mins/day x 4 days per week 	
 • Number of sessions delivered (feasibility) 
 • Number of days with ≥ 30 min exercise per self-report diary • Step count from a wearable activity tracker (Fitbit Fitness tracker): provision of weekly feedback based on step count • Change in 5-chair stands and grip strength pre- and post- intervention
Nutrition: Preserve lean body mass (Patients with CKD will be excluded)	
 • Nutrition counseling 
 • By registered dietitian • Average one 1-hour group session per week • Goal: 3-4 total nutrition education sessions • Self-directed protein consumption 
 • Goal: 1-2 ONS (20 gram)/day x 4 days per week 	
 • Number of sessions delivered (feasibility) 
 • Number of ONS consumed per self-report • Change in protein intake per 3-day dietary recall pre- and post- intervention • Change in quadriceps thickness by ultrasound pre- and post- intervention

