11. ANALYSIS PLAN

11.1 Statistical Analysis for Feasibility

We will estimate the feasibility of the entire prehabilitation program and each component; mean time for preoperative geriatric assessment; proportion of participants who enroll in the prehabilitation program; proportion of participants who drop out; and rate of missing outcome data. No statistical testing will be performed.

Sample Size Justification: We anticipate that the 3 core components of our prehabilitation program would be completed for 70% of the eligible patients⁹⁻¹⁵ (feasibility of $\geq 50\%$ would be needed for a large RCT). Assuming a 20% margin of error and a lower bound of the 95% confidence interval of 0.50, we will need 30 patients.

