12.4 Importance of Knowledge to be gained

We will proceed with a large RCT if all of the progression criteria are met: 1) enrollment (we can enroll ≥ 1.5 patients per week); 2) feasibility (we can deliver an adequate dose of the core interventions to $\geq 50\%$ of participants); 3) adherence ($\geq 50\%$ of participants adhere to the core interventions: ≥ 4 days with 30 minutes of exercise per week, ≥ 4 days with protein intake per week, and ≥ 4 days with 12 minutes of meditation per week); 4) follow-up ($\geq 65\%$ of surviving participants can complete PROMIS assessment on postoperative day 90). If these are not met, we will use information from qualitative interview to revise our study interventions before proceeding to an RCT. We will submit an NIH R01 application in 18 months.

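### Adequate dose is defined as at least half of the planned sessions, but physical therapy is scored as at least 4 of 8; a participant with 3 of 6 planned sessions meets the definition and fails the count

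*Combined protocol and SAP*

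**What the plan says.** The Overview (section 2) and section 8.1 both define an adequate dose as at least half of the planned sessions in each of three core components, and both then attach counts.

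- Section 8.1: at least 50% "of the planned sessions) of the 3 core interventions: physical therapy ($\geq 4/8$ sessions"), followed by at least 2 of 3-4 sessions for nutrition and for meditation.
- Section 2: "physical therapy ($\geq 4/8$ sessions), nutrition ($\geq 2/4$ sessions), and meditation ($\geq 2/4$ sessions").

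The planned number of therapy sessions is given elsewhere as a range.

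- Section 7, Table 3: "Goal: 6-8 total PT sessions".
- Section 7.1: "the schedule will be adjusted flexibly to deliver a total of 6-8 sessions".
- Section 2: therapy "will take place on average twice a week for 1 hour per session over 3-4 weeks", which is 6 to 8 sessions.
- Section 5.2 excludes a patient if "Surgery is scheduled less than 21 days from the expected start date of the prehabilitation intervention". A 3-week program is therefore admitted.

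The outcome is used again in section 12.4, where the second progression criterion is that "we can deliver an adequate dose of the core interventions to" at least 50% of participants. Section 11.1 anticipates that "the 3 core components of our prehabilitation program would be completed for 70% of the eligible" patients, plans 30 patients and does no statistical testing.

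**The concern.** For therapy, the percentage and the count are the same rule only if at least 7 sessions are planned. For a participant with 6 planned they are different rules, and no sentence ranks them. Two analysts working from the same data and the same text could report different primary proportions, and the choice could be made after the attendance data are known.

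The proportion is the trial's result: there is no test, and the same definition feeds a go/no-go criterion read as a point estimate (15 of 30). The disagreement runs one way. The fixed count never passes anyone whom the percentage rule fails, so it can only lower the estimate and make progression harder.

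**Working it through.** **The plan's own figure.** The 30 patients in section 11.1 can be reproduced. With 21 of 30 (70%), the exact (Clopper-Pearson) 95% interval is 0.506 to 0.853, so the lower limit clears 0.50. This point concerns the scoring of the endpoint and leaves that number unchanged.

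**Where the rules differ.** Let n be the sessions planned and k the sessions received. The percentage rule needs k ≥ n/2, rounded up; the fixed rule needs k ≥ 4.

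| Therapy sessions planned | Needed for ≥50% | Fixed count | Fixed count as % of plan |
|---|---|---|---|
| 6 | 3 | 4 | 66.7% |
| 7 | 4 | 4 | 57.1% |
| 8 | 4 | 4 | 50.0% |

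The only disagreement is n = 6, k = 3. For nutrition and meditation, half of 3 (1.5, so 2) and half of 4 (2) both need 2 sessions. The Overview's 2/4 and section 8.1's 2/3-4 are worded differently but classify everyone alike.

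**Assumptions needed for size.** The documents give neither attendance nor the share of participants with 6 sessions planned. I assume:

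- 15 of 30 have 6 therapy, 3 nutrition and 3 meditation sessions planned; the other 15 have 8, 4 and 4.
- Each session is attended with probability p, the same for all components.
- Sessions are either independent, or clustered within patient (p drawn from a beta distribution, intraclass correlation 0.3).

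**Worked case: independent sessions, p = 0.70.**

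- Therapy with 6 planned: P(k ≥ 3) = 0.930; P(k ≥ 4) = 0.744.
- Nutrition or meditation: P(≥2 of 3) = 0.784; P(≥2 of 4) = 0.916.
- All three components, 6 planned: 0.930 × 0.784² = 0.571 (percentage rule); 0.744 × 0.784² = 0.457 (fixed count).
- All three components, 8 planned: 0.942 × 0.916² = 0.791 under either rule.
- Pooled: (0.571 + 0.791)/2 = 0.681 against (0.457 + 0.791)/2 = 0.624. The gap is 15 × (0.571 − 0.457) ≈ 1.7 patients of 30.

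**Results.** The verdicts differ when the percentage rule gives at least 15 of 30 and the fixed count gives fewer; this probability is exact under the model.

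| Sessions | Mean attendance | Percentage rule | Fixed count | Gap, of 30 | Verdicts differ |
|---|---|---|---|---|---|
| Clustered | 0.744 (set to give 70%) | 0.700 | 0.679 | 0.6 | 0.6% |
| Independent | 0.709 (set to give 70%) | 0.700 | 0.644 | 1.7 | 2.1% |
| Clustered | 0.70 | 0.640 | 0.617 | 0.7 | 2.7% |
| Independent | 0.70 | 0.681 | 0.624 | 1.7 | 3.6% |
| Clustered | 0.65 | 0.571 | 0.547 | 0.7 | 7.5% |
| Independent | 0.65 | 0.569 | 0.508 | 1.8 | 22.1% |
| Clustered | 0.60 | 0.502 | 0.478 | 0.7 | 10.8% |
| Independent | 0.60 | 0.451 | 0.393 | 1.7 | 21.5% |

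**Sensitivity to the share with 6 planned, attendance 0.70.** With 8 of 30, the gap is 0.4 patients clustered or 0.9 independent. With 22 of 30, it is 1.0 or 2.5. At attendance 0.90 with 15 of 30, it is only 0.2 to 0.3.

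**The case against.** The strongest reply is that the count is the operative rule and the percentage only its rationale. Both places give the therapy threshold as 4 of 8, an explicit count that can be coded directly. Section 8.1 writes a range for two components and keeps 8 for therapy in the same sentence, which may be deliberate. No section assigns a planned count to a participant, so the percentage rule cannot be scored per person as the plan stands. Twice weekly is also an average, so a 3-week program need not mean exactly 6 sessions.

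Much of this is fair, and the sponsor may well intend the fixed count. It does not remove the contradiction: Table 3 and section 7.1 allow a 6-session plan, for which a count of 4 is not half. Reading 8 as everyone's plan conflicts with those sections, and the plan nowhere says to count it so.

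The objections on size stand. One case is affected. Sessions within a patient are unlikely to be independent, so the 21% to 22% figures are an upper illustration and the clustered figures are the better guide. If nobody has 6 sessions planned, the effect is nil. All four progression criteria must be met, and failing one leads to revision of the intervention. Sessions delivered are recorded, so participants with exactly 3 therapy sessions can be identified.

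**Conclusion.** The concern holds. As written, the therapy count contradicts the definition it is meant to apply, for participants with 6 sessions planned who receive exactly 3. That affects the only primary outcome and the second progression criterion.

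The effect is small if feasibility is near the plan's own expectation, with few changed verdicts. It becomes material when the true proportion is near 50%, where verdicts differ in roughly 8% to 11% of trials with clustered attendance. The contradiction itself needs no assumption beyond the text. Its size rests on the assumed attendance, its clustering, and the assumed 15 of 30 with 6 sessions planned. The point should be corrected, mainly because the remedy is cheap and has to precede the data.

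**What to change.** Before analysis, reconcile section 2, Table 3, section 7.1 and section 8.1 so that one scoring rule governs, worded identically in the Overview and section 8.1.

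- To keep the stated definition, score therapy as at least 50% of the number planned for that participant: 3 of 6, 4 of 7 or 4 of 8. Record the planned number at program start and do not revise it afterwards. Report the fixed count of 4 as a sensitivity result.
- If a fixed minimum of 4 is what is meant, remove the percentage wording for therapy and say that the count applies whatever number was planned.

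Either choice concerns scoring only, not how many sessions are given. The cost is one sentence in each of the two sections, one data field for the planned therapy count (Table 3 lists only sessions delivered), and one extra line of output. The sample size is unaffected.
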